### **Analysis of SKNA and QOL**

Subcutaneous nerve stimulation achieves its effects through neuromodulation, resulting in reduced sympathetic nerve activity. A non-invasive method to measure sympathetic nerve activity is through the skin sympathetic nerve activity (SKNA) recording. We will record SKNA using two different equipment. The first is ME6000 which makes high fidelity SKNA recordings with 10,000 Hz sampling rate. However, ME6000 is not sufficiently portable for ambulatory recordings. Therefore, we added Bittium Faros recorder for ambulatory recording at 1,000 Hz sampling rate.

The quality of life (QOL) is measured using the standard questionnaire to assess the overall effects of treatment on the study subjects.

SKNA recorded with ME6000 at rest and during 6-minute walk will be summarized at each time point using mean and standard deviation.

SKNA recorded with Bittium Faros when patients were ambulatory will be summarized at each time point using mean and standard deviation.

Quality of life (AFEQT-AF, EQ-5Q-5L) will be summarized by item and by overall score at the following time points, baseline, 3 week and 3-month visits using mean and standard deviation.

Change in the average values of SKNA (aSKNA) recording at rest on the procedure day from the baseline will be compared between the randomization groups using the Wilcoxon Rank Sum test. Values of aSKNA recording in ambulatory subjects and during 6-minute walk at baseline, 1 week, 2-week, 3 week and 3-month visits will be compared between randomization groups using linear mixed models, with Group, Week and Group-Week interaction as fixed effects, and a random intercept per subject. Week will be coded first as a categorical variable. If aSKNA appear to be linear in time, we may model Week as a continuous fixed effect. Missing at random will be assumed in the above stated linear mixed models. Additionally, the strategy of last-value-carried-forward (LVCF) will be employed to fill in missing data values as an alternative to the missing-at-random assumption and the linear mixed models will be re-

run. The LVCF analysis serves as a sensitivity analysis. Similar analyses will be performed for SKNA during 6-minute walk.

We will compare the number of Apple watch-detected AF episodes between week-3 and the end of study between Group A and Group B to test the null hypothesis that there are no differences in detected AF episodes between the two groups. For each patient, we will record the number of days that the patient is under observation, and the number of days that AF episodes are detected. Assuming that each patient's data follows a binomial distribution and the probability of AF daily detection is the same within group. Since patients' data are independent from each other and the sum of independent binomials are still a binomial, we can compare the two groups as two binomials with potentially different rates of AF detections. Fisher's exact test will be performed for this comparison at a two-sided significance level of 0.05.

The overall scores of Quality of life (AFEQT-AF, EQ-5Q-5L) questionnaires will be compared at the following time points, baseline, 3 week and 3 month visits by the same linear mixed effect models as described for aSKNA. The same missing data treatment as stated above will be employed in the linear mixed model analyses of these two outcomes. Item and total scores may be transformed if deemed necessary to fulfil model assumptions.

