### 1.3 SCHEDULE OF ACTIVITIES (SOA)

	Eligibility visit	Baseline	Procedure Day (lead implant) and post-operative observation****	1-week visit****	2-week visit****	3-week visit****	3-month visit*****
Screening and eligibility	x						
Obtain Informed consent	x						
Medical history/demographics		x					
Height/Wt/BMI		x					
Hospital Admission			x				
12 Lead EKG		x	x	x	x	x	x
INR (in subjects taking Coumadin)		x	x				
Pre-op instructions		x				x b	
Pregnancy test-Blood or urine for females with childbearing potential			x				
Pre procedure antibiotic			x				
Surgical Implantation			x				
Randomization (after surgery)			x				
Apple Watch Monitoring		x	x	x	x	x	x
Telemetry			x				
NeuroStimulator programming			x				
SKNA recording at rest		x	x	x	x	x	x
SKNA recording during 6-min walk*		x		x	x	x	x
Mental Math Test **		x		x	x	x	x
Discharge/patient teaching***			x				
Removal of Lead					x		

Echocardiogram	x					x	x
Mobile Cardiac Telemetry	X a		x	x	x		x
AFEQT-AF QOL questionnaire		x				x	x
EQ-5D-5L QOL questionnaire		x				x	x
CBC		x				X b	x
BMP		x				X b	x
BNP		x					x
Catecholamine levels		x					x
Subject Stipend	x	x	x	x	x	x	x
Subject Parking fee	x	x	x	x	x	x	x
Assess for Serious Adverse events and Adverse Events	x	x	x	x	x	x	x

The materials and the times of collection for Aim 1A. Labs=laboratory tests; CBC=complete blood count; BMP=basic metabolic panel; BNP=B type natriuretic protein; INR=international normalized ratio. \*if subject is able to complete, \*\*will complete only if unable to complete 6 min walk, \*\*\*discharge day is based on PI decision. \*\*\*\* will only be repeated for control subjects that crossover to experimental group \*\*\*\*\*will only be done on experimental group and control subjects that do not cross over a. Eligibility 7-Day Mobile Cardiac Telemetry is available for potential subjects who may not have had an ePatch monitor completed b. will only be repeated by the crossover group before second procedure

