### 6.3 MEASURES TO MINIMIZE BIAS: RANDOMIZATION AND BLINDING

The patient will be consented to undergo surgery. After the device implantation, the patients will be randomized to experimental and control groups using Redcap. We will attempt to blind the patients, although the tingling or pain associated with the stimulation may make blinding difficult. All data analyses performed by the co-investigators and the rhythm analyses performed by the Mobile Cardiac Telemetry system technicians will be blinded. The experimental group will receive stimulation at 3.5 mA output, while the control group will receive no stimulation. Data will be obtained during this time to determine atrial arrhythmia frequencies in both groups. The device will then be removed at the end of the second week. After the third week, we will give the option to the control group to crossover to the experimental group. This group of patients will undergo a second procedure to receive stimulation at 3.5 mA and we will follow up for another 3 weeks and 3 months post second procedure.

We will tell the patients that they will be randomized into experimental group or control group during surgery. We will attempt to blind the patients, although the tingling or pain associated with the stimulation may make blinding difficult. We will explain to all patients they may or may not feel tingling and/or pain during the 2-week stimulation time but will not tell them which group they are assigned to. All data analyses performed by the co-investigators and the rhythm analyses performed by the 7-day non-invasive monitoring system technicians will be blinded. After 3 weeks post-procedure, we will unblind the control group to give them the option of crossing over to the experimental group to receive the treatment. If they agree, these group of patients will forego the 3-month follow-up visit and will proceed with a second procedure along with follow up visits post-second procedure. Data will be obtained during this time to determine AF burden in all groups.

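### The LVCF sensitivity analysis has no exception for crossover controls, whose 3-month aSKNA and QoL values are missing by design in Group B only, so it can bias the 3-month contrast in either direction

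*Combined protocol and SAP*

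**What the plan says.** Section 9.4.3 (Analysis of SKNA and QOL) compares ambulatory and 6-minute-walk aSKNA at baseline, weeks 1, 2 and 3 and month 3 by a linear mixed model with group, categorical week and their interaction. For the main analysis, "Missing at random will be assumed in the above stated linear mixed models". In addition, "the strategy of last-value-carried-forward (LVCF) will be employed to fill in missing data values as an alternative to the missing-at-random assumption", and "The LVCF analysis serves as a sensitivity analysis". The AFEQT and EQ-5D-5L overall scores, taken at baseline, week 3 and month 3, follow the same route: "The same missing data treatment as stated above will be employed in the linear mixed model analyses of these two outcomes".

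Section 6.3 offers controls a crossover after week 3. Of those who accept, it says "these group of patients will forego the 3-month follow-up visit and will proceed with a second procedure". The Schedule of Activities (Section 1.3) agrees: its footnote on the 3-month visit says it "will only be done on experimental group and control subjects that do not cross over". Section 6.3 also says of the crossover patients that "we will follow up for another 3 weeks and 3 months post second procedure", which does not fit that footnote.

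Section 9.4.3 does not define the last value, does not exempt crossover patients from LVCF, and does not say whether data after the second procedure count as Group B data.

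**The concern.** A sensitivity analysis should show whether a result depends on the missing-at-random assumption. Here the 3-month gap is structural and lies in one arm. Group A and the controls who stay keep a true 3-month value. A crossover control is given a value from week 3, one week after the lead came out. If untreated patients change between week 3 and month 3, that change is present in Group A but absent from the filled sham values, and the difference looks like a treatment effect.

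Such a change is plausible, most of all for QoL. The week-3 score closely follows two weeks of restricted bathing, driving and lifting (Section 5.3). Patients are kept masked only until the primary endpoint is complete (Section 4.1), so Group A may answer the 3-month questionnaire unmasked, while the carried sham score comes from the masked period.

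The word last is also open. Section 1.2 normally places the second procedure within two weeks of the week-3 visit, so its repeat visits fall before month 3. Read literally, LVCF could put a value recorded after active stimulation into the sham 3-month cell.

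At stake is the comparison that bears on whether any aSKNA or QoL effect lasts beyond stimulation.

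**Working it through.** **Inputs from the documents.** The plan states no figure for the 3-month aSKNA or QoL comparison. The arm sizes come from Section 9.2, whose figure reproduces. The effect size is (76.3 − 5)/44.8 = 1.59. About 10 evaluable patients per arm are needed for 80% power at two-sided 0.025 with the Wilcoxon test (simulated power 0.83 at 10). Then 10/0.70 = 14.3, rounded up to 15. I use 15 per arm, and 10 per arm for 70% retention. There are five visits for aSKNA and three for QoL.

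**Assumptions, not in the documents.** Crossover share f of 0.4 to 1.0; untreated change d from week 3 to month 3 of 0 to 0.5 SD, the same in both arms; within-patient correlation 0.5 to 0.7; no treatment effect; crossover unrelated to outcome unless stated; nominal two-sided 5% test.

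**Bias.** Let m be the untreated sham mean at month 3.

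- Sham mean after LVCF = (1 − f)·m + f·(m − d) = m − f·d.
- The contrast (A minus B) therefore moves by +f·d.
- At f = 0.8, d = 0.5 SD: 0.8 × 0.5 = 0.40 SD.
- At f = 0.4, d = 0.25 SD: 0.4 × 0.25 = 0.10 SD.
- At d = 0: no bias.

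A negative d reverses the sign.

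**False-positive rate of the LVCF run.** 20,000 simulated null trials per cell, random-intercept model, baseline-to-month-3 group contrast, correlation 0.6:

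| Outcome | n per arm | d (SD) | f = 0.4 | f = 0.8 | f = 1.0 |
|---|---|---|---|---|---|
| QoL, 3 visits | 15 | 0 | 5.8% | 6.9% | 7.4% |
| QoL, 3 visits | 15 | 0.25 | 7.0% | 12.0% | 15.8% |
| QoL, 3 visits | 15 | 0.5 | 10.3% | 26.3% | 38.6% |
| QoL, 3 visits | 10 | 0.5 | 8.6% | 19.9% | 28.6% |
| aSKNA, 5 visits | 15 | 0 | 5.4% | 5.4% | 5.5% |
| aSKNA, 5 visits | 15 | 0.25 | 5.9% | 10.2% | 12.9% |
| aSKNA, 5 visits | 15 | 0.5 | 9.2% | 23.9% | 35.0% |
| aSKNA, 5 visits | 10 | 0.5 | 8.1% | 17.6% | 25.0% |

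Varying the correlation from 0.5 to 0.7 at f = 0.8 and d = 0.5 SD gives 23-32% for QoL and 20-30% for aSKNA at 15 per arm, and about 15-24% across both outcomes at 10 per arm.

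**Selective crossover.** If the controls with the highest week-3 values cross over, LVCF is biased by −0.10 to −0.15 SD even at d = 0, through regression to the mean.

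**Comparison with missing at random.** With crossover controls' data kept to week 3 and the rest left missing, the bias is within 0.01 SD when crossover is unrelated to outcome. At 15 per arm and correlation 0.6, the SD of the contrast is 0.36 at f = 0.4 and 0.49 at f = 0.8, against about 0.33 for LVCF. At f = 1.0 Group B has no untreated 3-month data. The categorical-week contrast then cannot be estimated, yet LVCF still returns a number made wholly of carried values.

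**Timing of the last value.** A second procedure at weeks 3 to 5 puts its repeat week 1-3 visits at about weeks 4 (3 + 1) to 8 (5 + 3), before month 3.

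**The case against.** The strongest reply is that LVCF is only a sensitivity run, on secondary endpoints reported with nominal p values. False support needs the main model to be positive too. In null simulations with three visits, 60% or 80% crossover and d up to 0.5 SD, the missing-at-random model rejected in 4-6% of trials, and both runs rejected together in only 1.5-3.1%. In the other false-positive cases LVCF would disagree with the main model, which would itself warn the reader. This stands, and it limits the damage. It does not rescue the LVCF run, which answers a question about missing-data assumptions with an error of its own.

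Three stronger readings are tempting, and the documents do not support them:

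- A reader might infer that the whole sham arm is frozen at week 3 and that false differences must follow. Controls who do not cross over keep a real 3-month visit, and bias needs either change after week 3 or selective crossover. The bias can also hide a true effect.
- A reader might infer that the carried value is certainly the week-3 value. The plan leaves that open.
- A reader might infer that LVCF carries on-stimulation values forward for Group A drop-outs on every outcome. That is possible for aSKNA but not for QoL, which is first repeated at week 3, after lead removal.

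The understated standard error is also a small matter: with no drift the rate is 5.4-5.5% for aSKNA and about 6-7% for QoL.

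**Conclusion.** The point holds as a conditional defect in a stated rule. LVCF as written applies to values that are missing by design in one arm, and it biases the 3-month contrast by f × d. The size rests on a crossover share and a drift that the documents do not give. High uptake is plausible, since Section 10.4 says the option was added to help recruitment, but 80% and 0.5 SD remain illustrations.

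The reach is limited to the LVCF re-runs for ambulatory and 6-minute-walk aSKNA and the two QoL scores at 3 months. A reader might infer a threat to the trial's main efficacy result. There is none from this source: the primary analysis of week-1 AF burden and the main mixed models use no carried values. The change should be made, but it is not critical to the trial.

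**What to change.** In Section 9.4.3, for aSKNA and both QoL scores:

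1. State that LVCF is not applied to values missing because of crossover, and that values recorded after the second procedure are not used as Group B values.
2. Keep crossover controls' data up to week 3 in the planned missing-at-random mixed model. This is better than comparing Group A with the non-crossover controls alone, who are self-selected and unblinded.
3. Label the 3-month contrast exploratory and show the number of controls who did not cross over.
4. Replace LVCF by a delta-adjusted (tipping-point) analysis as the departure from missing at random, with the range of deltas fixed in advance.
5. Reconcile Section 6.3 with the Schedule of Activities footnote on 3-month follow-up after crossover.

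The cost is wording plus IRB review, since the Statement of Compliance requires that review for any protocol amendment. The 3-month contrast becomes less precise and openly rests on few controls: at 15 per arm and 80% crossover, 15 − 12 = 3. If all controls cross over it cannot be estimated with categorical week, and the report should say so.

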### 9.2 SAMPLE SIZE DETERMINATION

The AF burden is determined by the amount of time spent in AF detected by Mobile Cardiac Telemetry patch. A recent study analyzed the results of ambulatory single-lead ECG patch sensor monitoring for 11.4 days on average in 7934 men and 5359 women with paroxysmal AF. During the monitoring period, there were a total of 1,041,504 paroxysmal AF episodes. The median daily rate of paroxysmal AF was 1.21 episodes per day (interquartile range [IQR] 0.31-4.99), and the median maximum duration per individual was 7.5 hours (IQR 2.4-18.6 hours). The median burden of AF (% of time in AF relative to entire period of monitoring) was 8.9% (IQR 3.4%-25.2%). Assuming that we implant the lead and randomize patients into experimental group (stimulation) and control group (no-stimulation), we expect to see the same average AF burden among our patients. In our previous study in canine models, subcutaneous nerve stimulation reduced atrial arrhythmia burden per 48 hours from  $211.0 \pm 204.8$  s to  $134.8 \pm 165.2$  s ( $\Delta = -76.3 \pm 44.8$  s) versus a reduction of  $-5 \pm 9.5$  seconds in the sham group. Assuming the same standard deviation of the change of AF burden from baseline in the two randomized groups as 44.8 and accounting for the patient retention rate of 70%, we need 15 per arm (total 30 patients) for 80% power at 2-sided alpha 0.025 to detect an effect size of 1.59 at the end of one week between Group A (experimental) and Group B (control) using the Wilcoxon rank sum test. If the treatment suppresses AF by 75% while the sham does not suppress AF at the end of one week, we have 86% power to detect this difference at 2-sided alpha 0.025 using Fisher's exact test. We have budgeted for 32 patients to ensure that we have sufficient funds to complete the study.

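### The Apple Watch comparison pools patient-days into one binomial per arm, so its nominal 5% Fisher test has a false-positive rate of roughly 20% to 75%

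*Combined protocol and SAP*

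**What the plan says.** The test is in section 9.4.3 of the combined protocol and SAP, under the heading Analysis of SKNA and QOL. The aim is stated as "We will compare the number of Apple watch-detected AF episodes between week-3 and the end of study between Group A and Group B". The data for each patient are day counts: "we will record the number of days that the patient is under observation, and the number of days that AF episodes are detected". The null hypothesis is therefore worded in episodes, while the tested quantity is days with a detection.

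The plan then assumes that "the probability of AF daily detection is the same within group". It argues: "Since patients' data are independent from each other and the sum of independent binomials are still a binomial". It concludes that "we can compare the two groups as two binomials with potentially different rates of AF detections", and adds: "Fisher's exact test will be performed for this comparison at a two-sided significance level of 0.05". The only independence it claims is between patients. Nothing in the paragraph deals with correlation among one patient's days, or with patients in the same arm having different rates.

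Section 9.2, in setting the sample size, reports for a large cohort with paroxysmal AF: "The median daily rate of paroxysmal AF was 1.21 episodes per day (interquartile range [IQR] 0.31-4.99".

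**The concern.** A sum of binomial counts is itself binomial only when all of them share one probability. Each patient's count is binomial only when that patient's days are independent. Paroxysmal AF fails the first condition on the protocol's own figures, because some patients have AF on most days and others rarely. Detection adds further differences: under section 8.1 patients wear the watch as much as they can, ECG recordings are optional, and the high heart rate alert is set patient by patient.

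When patients differ, 70 days from one patient carry much less information than 70 independent observations. Fisher's test does not know this and uses a standard error that is too small. A chance imbalance of a few frequent-AF patients between arms then appears as a significant difference, in whichever direction the imbalance fell.

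Section 9.4.3 makes p-values nominal unless otherwise stated, and this test is given a formal level. It covers the period between the 3-week and 3-month visits, so it would be cited for or against a lasting effect after stimulation ends.

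**Working it through.** **Inputs**

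- Level: two-sided 0.05 (section 9.4.3).
- Patients: 15 per arm with 70% retention (section 9.2); 15 × 0.70 = 10.5, so about 10 evaluable per arm.
- Days per patient, m: not stated. From week 3 to week 12 is 9 × 7 = 63 days; to 13 weeks is 10 × 7 = 70; with the final 7-day monitoring, 77. The base case is 70, or about 10 × 70 = 700 patient-days per arm.
- ICC among one patient's days: not in the documents. Assumed range 0.01 to 0.50, plus a value derived from section 9.2.

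**1. The plan's own figure.** With one common daily probability (0.1, 0.3 or 0.5), independent days, m = 70 and 15 or 10 patients per arm, the pooled Fisher test rejects a true null in 4.2% to 5.1% of simulated trials. The stated 5% is correct under the plan's assumption.

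**2. Allowing correlation.** The design effect is DE = 1 + (m − 1) × ICC, and the actual error is about 2 × [1 − Φ(1.96 / √DE)]. At ICC 0.02, DE = 1 + 69 × 0.02 = 2.38, 1.96 / √2.38 = 1.27, and the error is 0.20. Beta-binomial simulation of the Fisher test itself (2,000 trials per cell; ranges are over daily probabilities 0.1, 0.3 and 0.5) agrees:

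| ICC | DE | Formula | Simulated, 15 per arm | Simulated, 10 per arm |
|---|---|---|---|---|
| 0.01 | 1.69 | 0.13 | 0.12–0.14 | 0.11–0.14 |
| 0.02 | 2.38 | 0.20 | 0.20–0.21 | 0.18–0.20 |
| 0.05 | 4.45 | 0.35 | 0.33–0.35 | 0.33–0.35 |
| 0.10 | 7.90 | 0.49 | 0.46–0.47 | 0.45–0.48 |
| 0.20 | 14.80 | 0.61 | 0.61–0.62 | 0.60–0.62 |
| 0.30 | 21.70 | 0.67 | 0.67–0.69 | 0.66–0.68 |
| 0.50 | 35.50 | 0.74 | 0.73–0.75 | 0.73–0.75 |

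At ICC 0.50, 700 patient-days are worth 700 / 35.5 ≈ 20 independent ones. Over ICC 0.02 to 0.50 the formula gives 0.19 to 0.73 with 63 days and 0.22 to 0.75 with 77. With 10 against 3 patients, as might follow from crossover, simulation gives 0.19–0.21 at ICC 0.02 and 0.74–0.77 at 0.50.

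**3. The ICC implied by section 9.2.** Take patients' daily rates as lognormal with median 1.21 and log SD = ln(4.99 / 0.31) / 1.349 = 2.06. With Poisson episodes, the probability of an AF day is 1 − exp(−rate): 0.27, 0.70 and 0.99 at the lower quartile, median and upper quartile. With ICC = Var(p) / [p̄(1 − p̄)]:

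| Share of episodes detected | ICC | Error, 15 per arm | Error, 10 per arm |
|---|---|---|---|
| 100% | 0.55 | 0.75 | 0.75 |
| 30% | 0.53 | 0.74 | 0.76 |
| 10% | 0.48 | 0.73 | 0.73 |
| 3% | 0.41 | 0.71 | 0.73 |
| 1% | 0.32 | 0.67 | 0.66 |

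A shorter window helps little. With 30 days and ICC 0.55, DE = 1 + 29 × 0.55 = 16.95 and the error is about 0.63.

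**4. One value per patient.** A Wilcoxon rank sum test on each patient's proportion of AF days gives 3.9% to 5.3% for ICC 0.02 to 0.50 with 15 or 10 per arm, and 4.5% to 4.8% under the section 9.2 model with all episodes detected (3,000 trials per cell).

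**The case against.** - **Standing of the test.** Watch-detected AF is not among the listed endpoints, and section 8.1 calls the watch a secondary monitoring system. The primary test in section 9.4.2 is already a patient-level Wilcoxon test. This stands: the trial's main conclusion does not depend on the pooled test.
- **A patient-level model already exists.** Section 9.4.2 plans a linear mixed model with a random intercept per subject for the reduction in watch-detected episodes from baseline over the same period, and allows GEE instead. This is true and should be credited. It answers a related question, though, and does not replace the section 9.4.3 test, whose p-value would still be reported.
- **The ICC is unknown.** This also stands. At ICC 0.01 the error is 11% to 14%, and it exceeds one half only above about 0.11, since (1.96 / 0.674)² = 8.44 and (8.44 − 1) / 69 = 0.108.
- **The section 9.2 spread is on another scale.** It is in episodes per day on a continuous patch. The 16-fold contrast (4.99 / 0.31) shrinks to less than four-fold in daily probability (0.99 / 0.27), and the cited cohort may be more varied than the enrolled patients. This is fair, but the calculation above is done on the probability scale, and even 1% detection leaves the error near 66%.
- **Crossover.** Under section 6.3, Group B patients may be unblinded and receive active stimulation within the same window. That is a separate problem, which changing the unit of analysis does not solve.

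**Conclusion.** The concern holds. The pooled Fisher test treats correlated days as independent observations, and its stated 5% level depends on a common-probability assumption that the protocol's own figures contradict. With about 70 days per patient the false-positive rate is roughly 20% to 75% for ICCs from about 0.02 to 0.53. The section 9.2 spread points to the upper end, 66% to 76%, so under the protocol's own figures the test would more often than not declare a difference when there is none.

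The size rests on an assumed or derived ICC, a derived window of 63 to 77 days, and a constant daily rate within each patient. Clustering of AF days within a patient would make it worse. The number of patients per arm hardly matters. The damage is confined to this secondary watch comparison.

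**What to change.** In section 9.4.3, delete the pooled-binomial argument and the Fisher test. In their place, compute for each patient the number of days with AF detected divided by the number of days observed from week 3 to the end of study, and compare arms with a two-sided Wilcoxon rank sum test on those proportions. State how patients with few observed days are handled, and word the null hypothesis in the same unit as the test (days with AF, not episodes).

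A patient-level permutation test adjusted for the baseline watch proportion is a reasonable supporting analysis. It should stay supporting, because the version 8 entry in section 10.4 indicates that earlier patients have no watch data from before randomization. Aligning the paragraph with the subject-level mixed model or GEE of section 9.4.2 would also repair the unit of analysis, but GEE with about 10 patients per arm would need a small-sample correction.

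The same edit should say how days after Group B crossover are counted, since the new test does not settle that.

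The cost is one paragraph of SAP text and no new data. The p-value will generally be larger than the pooled test would give, because it reflects the number of patients actually randomized.

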**The following pairs of secondary null and alternative hypotheses will be tested:**

- 1) that the trajectories of reduction of AF burden by time between treatment and control groups are the same versus that the trajectories are different;
- 2) that reduction of AF burden in treatment group does not depend on time versus that the reduction of AF burden is dependent on time;
- 3) that effects of ScNS and sham stimulations on ventricular rate control during AF are the same for the treatment and the control groups versus that the effects are different between the two groups;
- 4) that reduction of SKNA is the same between the treatment and the control groups versus that the reduction of SKNA is different between the two groups;
- 5) that improvement of quality of life is the same between the treatment and the control groups versus that the improvements of QoL is different between the two groups.
- 6) There is a reduction of AF burden after crossing over from control to experimental group

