We may also use generalized estimating equations (GEE) instead of linear mixed effect models if the validity of the latter is suspect. If there is differential drop-out between the randomized groups, we will adjust the group-comparisons using baseline covariates, such as age, sex and heart failure status. Standard approaches for both model checking and selection based QIC will be applied.

---

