#### 9.4.3 ANALYSIS OF THE SECONDARY ENDPOINT(S)

The analyses of the secondary endpoints will be performed on the modified ITT data set. Unless otherwise stated, two-tailed nominal p values will be reported.

##### Analysis of mean VR at the end of week 1

In dogs, ScNS reduces ventricular rate during AF. The mean VR was  $149 \pm 36$  bpm after the induction of AF. The VR significantly decreased to  $84 \pm 16$  bpm ( $p=0.011$ ) at the final week of ScNS. The same device that produces AF burden will also generate VR. First, we will summarize the proportion of patients who are AF-free at the end of week 1. Fisher's exact test will be performed to test if the proportions of AF-free patients are the same between the two treatment arms at a two-sided significance level of

0.025. Second, we will summarize the mean VRs using mean and standard deviation by time and by randomization group among the patients who experience AF.

We will classify patients into 3 groups based on the week 1 average VR: patients who do not experience AF as category 1, patients who experience AF with VR  $\leq$  110 bpm as category 2, and patients who experience AF with VR  $>$  110 bpm as category 3. Fisher's exact test will be performed to test if the distribution of the three categories are the same between the two treatment arms and the nominal p-value will be reported.

We will categorize average VR at other time points into three groups as described above, and analyze repeated average VR using ordinal repeated measure analysis with patient as the blocking variable, week and group as well as their interaction as independent variables. Proportional odds assumption will be checked.

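### The quality-of-life and walk-aSKNA mixed models leave a free group difference at the pre-randomization baseline and do not name the contrast; this costs precision, not validity

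*Combined protocol and SAP*

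**What the plan says.** Section 9.4.3, under the analysis of SKNA and QOL, sets out the aSKNA model. The visits that enter as outcomes include the first one: "Values of aSKNA recording in ambulatory subjects and during 6-minute walk at baseline, 1 week, 2-week, 3 week and 3-month visits will be compared". The comparison is between arms, and the fixed and random effects are listed as "with Group, Week and Group-Week interaction as fixed effects, and a random intercept per subject". On coding, it says "Week will be coded first as a categorical variable"; a linear term may follow if the data look linear in time. The overall AFEQT and EQ-5D-5L scores "will be compared at the following time points, baseline, 3 week and 3 month visits by the same linear mixed effect models", which refers back to the aSKNA specification.

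The Schedule of Activities (section 1.3) places both questionnaires and the 6-minute-walk SKNA recording at the baseline visit. Randomization follows implantation on the procedure day.

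Neither paragraph enters the baseline value as a covariate or gives the arms a common baseline mean. The only covariate adjustment described in section 9.4 sits under the AF-burden analysis (9.4.2) and applies if drop-out differs between groups: "we will adjust the group-comparisons using baseline covariates, such as age, sex and heart failure status". Its examples do not include the baseline value of the outcome.

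The treatment contrast is not named. Section 9.4.3 speaks of comparing values at visits. Section 9.1 states a null hypothesis about change: "that improvement of quality of life is the same between the treatment and the control groups". For secondary endpoints, "Unless otherwise stated, two-tailed nominal p values will be reported"; these models are given no significance level, effect size, SD or correlation.

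**The concern.** When Week is categorical and fully crossed with Group, every visit has its own group difference, including the visit before randomization. Randomization makes the baseline means equal in expectation, so the model spends information estimating a difference known to be zero on average. What remains for week 3 is either the plain difference in week-3 means or the difference in change from baseline. Neither uses the estimated regression of outcome on baseline.

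Quality of life and SKNA are listed secondary endpoints in a trial planned for 30 patients at 70% retention. Chance baseline imbalance is common at that size. For a normal outcome, a baseline gap above 0.3 SD has probability P(|Z| > 0.3/√(2/15)) = P(|Z| > 0.82), about 41%, at 15 per arm, and about 50% at 10 per arm. The week-3 difference carries ρ times that gap; the change contrast over-corrects by (1 − ρ) times it. Because the contrast is open, the choice between the two could also be made after the data are seen.

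**Working it through.** **The plan's own figure.** There is none for these endpoints. The only sample-size figure is for AF burden (section 9.2), and it reproduces. d = (76.3 − 5)/44.8 = 1.59. At two-sided 0.025, 9 per arm gives 80.6% power by the t test. Dividing by the Wilcoxon efficiency 0.955 gives 9.4, so 10, and 10/0.7 = 14.3, so 15 per arm. It sets the size of the trial but says nothing about QoL or aSKNA.

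**Inputs.** From the documents: 15 per arm, 1:1 allocation, 70% retention (15 × 0.7 = 10.5, about 10 per arm), and the model of 9.4.3. Assumed: effect in SD units, baseline-to-week-3 correlation ρ, two-sided 0.05, equal variances across visits, complete data.

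**Variance factors** for the week-3 group comparison, in units of 2σ²/n:
- Free baseline, week-3 difference: 1
- Free baseline, difference in change: 2(1 − ρ)
- Common baseline mean: 1 − ρ²

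Since 1 − (1 − ρ²) = ρ² ≥ 0 and 2(1 − ρ) − (1 − ρ²) = (1 − ρ)² ≥ 0, the third is never larger than either of the others.

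**Power.** Noncentral t with noncentrality d/√(2V/n). For the adjusted analysis, V = (1 − ρ²)(1 + 1/(2n − 4)), which allows for estimating the slope. Example at n = 15, d = 1, ρ = 0.5: free baseline, 1/√(2/15) = 2.739 on 28 df, power 75.3%; adjusted, V = 0.75 × (1 + 1/26) = 0.779, 2.739/√0.779 = 3.10 on 27 df, power 84.9%.

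Effect 1 SD, 15 per arm:

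| ρ | Factors (week-3 / change / common) | Week-3 difference | Change | Common baseline |
|---|---|---|---|---|
| 0.3 | 1 / 1.40 / 0.91 | 75.3% | 60.8% | 77.5% |
| 0.5 | 1 / 1.00 / 0.75 | 75.3% | 75.3% | 84.9% |
| 0.7 | 1 / 0.60 / 0.51 | 75.3% | 92.7% | 95.2% |

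Other effect sizes at ρ = 0.5:

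| Effect | 15 per arm | 10 per arm |
|---|---|---|
| 0.5 SD | 26.2% to 32.2% | 18.5% to 21.9% |
| 1 SD | 75.3% to 84.9% | 56.2% to 65.6% |
| 1.59 SD | 98.7% to 99.7% | 91.9% to 96.3% |

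**Cross-checks.** If the planned contrast has 80% power at ρ = 0.5, the normal approximation for the adjusted one is Φ[(1.960 + 0.842) × √(1/0.75) − 1.960] = Φ(1.275) = 89.9%. REML fits of the random-intercept model were also simulated (3 visits, ρ = 0.5, 15 per arm, effect 1.023 SD, 1,500 trials). Power was 77% for the week-3 difference, 78% for change and 87% with a common baseline mean. Across all simulated settings, type I error was about 3% to 5% for every version.

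**The case against.** The strongest reply is that the planned model is a standard longitudinal analysis, unbiased under randomization with sound type I error. The plan claims no power for these endpoints and reports nominal p values, so no stated figure or decision rule is wrong. That stands: this is a matter of efficiency and specification.

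Three stronger readings are tempting, and the documents do not support them.

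- A reader might infer that baseline is discarded. Section 9.1 frames the hypotheses as improvement in QoL and reduction in SKNA, which points to the Group-by-Week contrast, and that contrast does subtract baseline. What is left is a slope fixed at 1 rather than estimated. Section 9.4.3 also assumes missing at random, so where later visits are missing, baseline still informs the fit. The 10-per-arm figures treat retained patients as complete cases and are illustrative only.
- A reader might infer a fixed loss of about 10 points. That needs ρ near 0.5 and an effect near 1 SD, and the documents give neither. At ρ = 0.5 the two planned contrasts happen to have equal variance; elsewhere they differ. If the contrast in use suits the correlation, the gain at 1 SD is only about 2 points (week-3 difference at ρ = 0.3; change at ρ = 0.7).
- A reader might infer that the point covers ambulatory aSKNA. The model sentence does, but the schedule places mobile telemetry at eligibility (optional) and from the procedure day on, not at the baseline visit. The point is therefore confined to QoL and walk aSKNA.

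One further limit: the inequality is for the large-sample factors. At 15 per arm the slope-estimation term 1 + 1/26 makes adjustment marginally worse than the week-3 difference when ρ is below about 0.19, and marginally worse than change when ρ is above about 0.93.

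**Conclusion.** The point holds as one of precision and of an unnamed contrast. For AFEQT, EQ-5D-5L and walk aSKNA, the model frees a group difference at a visit that precedes randomization, and a common baseline mean would usually sharpen the week-3 comparison. With a 1 SD effect and 15 per arm, the gain over the three correlations runs from about 2 to about 17 points against the change contrast, and from about 2 to about 20 against the week-3 difference. At ρ = 0.5 it is about 10 points for 1 SD, about 6 for 0.5 SD and about 1 for 1.59 SD. All of these rest on assumed effects, correlations and a 0.05 level. They say nothing against the validity of the planned test, and they do not concern the AF-burden analysis.

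**What to change.** In section 9.4.3, for AFEQT, EQ-5D-5L and walk aSKNA, drop the Group main effect so that both arms share one baseline mean. Keep Week, Group-by-post-baseline-Week terms and the random intercept. Name the week-3 Group contrast from that model as the comparison. Week 3 is the natural choice because section 6.3 has controls who cross over skip their first 3-month visit.

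Modelling post-baseline values with baseline as a covariate is a close alternative, but not an equivalent one: it drops patients with a missing baseline value. That can happen here, because the walk is done only by those able to complete it, and the modified intention-to-treat set (section 9.3) requires baseline AF burden but not baseline QoL or aSKNA. The plan should name one of the two.

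The cost is a sentence or two of SAP text and one changed model term. No patient, visit or measurement is added.
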